#### **5.5 Coronary angioplasty**

Coronary angioplasty will be performed according to common practice and to physician choice concerning lesion preparation, stent implantation, need for post-dilatation or adjunctive treatment strategies. In order to reduce possible confounding factors, the same coronary stent (i.e. Resolute Onyx, Medtronic) will be used for all subjects.

In the peri-procedural period, medications will be administered in line with applicable guidelines on PCI. In particular, during the index procedure heparin or bivalirudin will be used alternately as per the hospital standard of care; while GPIIb/IIIa blockers will be left to the discretion of the operator. Accordingly, subjects will be adequately loaded with dual antiplatelet therapy (DAPT).

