## 2 STUDY DESCRIPTION

This is Sponsored, prospective, single-center, randomized study. Subjects who meet eligibility criteria are randomly assigned (1:1) to manual PCI (n=33) or robotically-assisted PCI (n=33). In both arms, the final result will be evaluated by IVUS assessment of ostial coverage.

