**2.2 Inclusion criteria**

1. Male or nonpregnant female aged  $\geq 18$  years
2. Coronary ostial lesions suitable for percutaneous coronary intervention (PCI).
3. The subject has been informed of the nature of the study, agrees to its provisions and has provided written informed consent.

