### Lesion relevant criteria

5. Ostial left main disease
6. Chronic Total Occlusion

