### **3 STATISTICAL DESIGN**

The present study is a prospective, randomized 1:1, single-center study. It is intended for subjects with indications of coronary revascularization and coronary lesions suitable for PCI. Subjects will be randomly assigned to one arm out of two: robotic PCI (n=33) or manual PCI (n=33) in a 1:1 ratio.

Based on previous studies, we estimated an overall incidence of geographic ostial miss of 50%. Assuming that the use of robotic PCI can selectively achieve at least a 70% reduction of the geographic miss, 66 subjects are required to have an 80% chance of detecting, as significant at the 5% level, a 70% decrease of geographic miss from manual PCI to robotic PCI arm.

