## 5.7 IVUS assessment

The secondary endpoint for the clinical study will be the distance from the proximal stent edge to the true ostium as measured by IVUS following stent deployment. The aorto-ostium will be defined as the plane at which the coronary artery joined the aorta sinus. Protrusion of the stent beyond this plane (*protruding stent*) as well as the distance between this plane and the most proximal stent strut (*geographical miss*) will be measured. In the case of side branches (left anterior

descending or circumflex) the ostium will be defined as the plane between the side branch emerging point and the carina tip. Protrusion of the stent beyond this plane (*protruding stent*) as well as the distance between this plane and the most proximal stent strut (*geographical miss*) will be measured.

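### A stent run across the LAD or circumflex ostium counts as full coverage whatever its accuracy, and the operator makes that choice after allocation is known

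*Combined protocol and SAP*

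**What the plan says.** - **Endpoint.** Section 2.1 makes full ostial coverage, on angiography and IVUS, the primary endpoint. It sets no limit on proximal extension. The distance from stent edge to ostium is a secondary endpoint (sections 2.1 and 5.7).
- **Lesions admitted.** Section 2.2 admits "Coronary ostial lesions suitable for percutaneous coronary intervention (PCI"). The lesion exclusions in section 2.3 are "Ostial left main disease" and chronic total occlusion. Section 5.7 brings LAD and circumflex ostia into scope with their own ostial plane, in the sentence that begins "In the case of side branches (left anterior".
- **Order of events.** Under section 5.4 the operator assesses the lesion and the subject is then randomised. Nothing requires the intended stent strategy to be written down first. Section 5.5 then leaves the procedure to "physician choice concerning lesion preparation, stent implantation, need for post-dilatation or adjunctive treatment strategies"; only the stent model is fixed.
- **Planning figures.** Section 3 states "we estimated an overall incidence of geographic ostial miss of 50" per cent, then "Assuming that the use of robotic PCI can selectively achieve at least a 70% reduction of the geographic miss", and concludes that "66 subjects are required to have an 80% chance of detecting, as significant at the 5% level". Section 2 has subjects "randomly assigned (1:1) to manual PCI (n=33) or robotically-assisted PCI (n=33").

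**The concern.** The rationale for the trial is positional precision: landing the proximal stent edge at the ostium, with neither a miss nor needless protrusion. Coverage measures that precision only when the operator is aiming at the ostial plane. If the stent is intentionally carried from the LAD or circumflex back into the left main, the ostium is covered by construction, and the result says nothing about manual or robotic accuracy.

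Two consequences follow. If crossing is equally common in both arms, it dilutes the contrast. If it is more common in one arm, it shifts the contrast. The second is the more serious, because the operator cannot be masked and chooses after allocation. Randomisation does not balance a choice made afterwards that itself determines the endpoint.

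**Working it through.** **Inputs from the documents.** Miss rate 50% with manual PCI; 70% relative reduction, so 0.50 × (1 − 0.70) = 0.15 with robotic PCI; 33 per arm; 5% level; 80% power (sections 2 and 3). Neither sidedness nor the test is stated.

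**Reproducing the plan's N.** Two-sided, two proportions, mean rate 0.325:

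- Without continuity correction: m = [1.960·√(2·0.325·0.675) + 0.842·√(0.50·0.50 + 0.15·0.85)]² / 0.35² = 26.9, so 27 per arm (54 in total).
- With continuity correction: (m/4)·[1 + √(1 + 4/(m·0.35))]² = 32.4, so 33 per arm (66 in total).

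The stated 66 is reproduced by the two-sided, continuity-corrected formula.

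**Model for crossing.** Let f be the share of an arm in which the stent is run across the ostium. Those cases cannot be misses, so the observed miss rate is the rate among the other ostia × (1 − f). For example, with f = 20% in both arms, 0.50 × 0.80 = 0.40 and 0.15 × 0.80 = 0.12. Every f is an assumption, because the documents give none.

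**Result.** Probability of a significant two-sided result at 5%, from full enumeration of two binomials of 33:

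| Scenario | Miss, manual vs robotic | Fisher exact | Uncorrected chi-square |
|---|---|---|---|
| Plan, no crossing | 50% vs 15% | 82% | 89% |
| 10% crossed in both arms | 45% vs 13.5% | 74% | 84% |
| 20% crossed in both arms | 40% vs 12% | 66% | 77% |
| 20% crossed, manual only | 40% vs 15% | 53% | 65% |
| 20% crossed, robotic only | 50% vs 12% | 90% | 94% |
| No true effect, no crossing | 50% vs 50% | 3.6% | 6.4% |
| No true effect, 20% crossed, robotic only | 50% vs 40% | 10% | 15% |
| No true effect, 30% crossed, robotic only | 50% vs 35% | 19% | 26% |

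Equal use shrinks the difference from 35 points to 28 at f = 20%. Unequal use moves it either way. With no true effect, f = 20% in the robotic arm alone produces a spurious difference of 10 points.

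**The case against.** **The comparison is of strategies.** Section 2.1 describes a strategy of robotic PCI against a strategy of manual PCI, and section 5.5 deliberately allows common practice. On that view, choices made after allocation belong to what is compared. This is a fair reason not to restrict the operator. It does not rescue the interpretation: the trial is justified by accuracy, and a difference produced by crossing would be read as accuracy.

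**The cause is the endpoint.** Crossing succeeds only because coverage has no proximal limit, and any long protrusion scores the same. This stands, and it is why the fix below addresses scoring and recording, not who may enter. Protrusion is also measured under section 5.7, so crossing should be visible in the IVUS data. But a secondary measurement does not protect the primary comparison, and it does not show whether crossing was intended before allocation.

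**Existing safeguards.** The investigator may exclude subjects unsuitable for robotic PCI (section 2.3), and lesion assessment precedes randomisation (section 5.4). The first concerns robotic feasibility. The second leaves no record of the planned landing point.

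**The 50% rate may not apply.** The only series with such a rate in section 1.1 (54%) is aorto-ostial and counts misplacement in both directions. No document gives a miss rate for branch ostia. This stands as a limit on the illustrations.

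**Previously stented ostia.** A reader might infer that a target ostium already carrying a stent would also be scored as covered automatically and so bias the result. The documents do not support that. Section 5.7 measures after stent deployment, which most naturally means the new stent. An old stent need not cover the ostium. The status is also fixed before randomisation, so it could dilute the comparison but not bias it systematically. What remains is that section 5.7 does not say explicitly which stent is measured.

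**Conclusion.** The concern holds for stents run across the LAD or circumflex ostium. The plan scores them as success whatever the accuracy, and leaves their use to an unmasked choice after allocation. No section prevents this, records the intention beforehand or examines its effect.

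The size and direction are unknown. The illustrations assume shares of 10% to 30%, the plan's own miss rates applied to all remaining ostia, and 33 evaluable subjects per arm. With 82% power by Fisher's exact test on the plan's own assumptions, there is little reserve for dilution.

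Two stronger conclusions are not supported. A reader might infer that the result will be biased towards robotic PCI; the documents give no ground for expecting more crossing in either arm. Nor is the sample size miscalculated: 66 follows from the stated inputs.

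**What to change.** None of these changes restricts treatment or eligibility.

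1. **Section 5.4.** Before randomisation, the operator records in the eCRF the target ostial lesion, the intended proximal landing point relative to the section 5.7 plane (at the ostium or across it), and whether that ostium already carries a stent.
2. **Section 5.7.** State that the measurement refers to the newly implanted stent.
3. **Section 3.** Keep every subject in the arm as randomised, and keep the section 2.1 endpoint as the single deciding primary analysis. Pre-specify a sensitivity analysis in which a stent extending across the ostial plane into the donor vessel is not counted as accurate placement. Add an analysis by the strategy recorded before randomisation, and report crossing by arm.

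The analysis by recorded strategy uses a characteristic fixed before allocation, so comparisons within each stratum remain randomised. These analyses do not remove the effect from the primary result; they show whether it depends on crossing. Excluding such lesions is not needed and could be costly: if 20% were excluded, 18 months of enrolment would become 18/0.80 = 22.5 months.

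Cost: one extra eCRF entry and a small amount of analysis. It has to be done prospectively, because intention cannot be reliably reconstructed after the procedure.

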## 5.6 Manual Conversion for Robotic-assisted PCI

Unplanned manual conversion (UMC), defined as a disengagement of the robotic drive to use bedside manipulation of either the guide catheter, guidewire, or delivery system and that was due to:

- Inability to navigate to the target lesion as intended, cross the target lesion as intended, treat the target lesion as intended, retract the CorPath GRX system as intended, or other CorPath system device malfunction; OR
- Any clinical condition that requires rapid medical intervention

In the context of this study, a manual conversion will be considered to have occurred if a subject is randomized to robotic-assisted PCI and the operator converts from robotic PCI to manual PCI when treating the ostial lesion(s). In both study arms, non-target lesion(s) (lesions not located in the ostium) may be treated manually or robotically at the primary operator's discretion. Manual conversion can only occur intraprocedural. Reasons for manual conversion should be recorded in the eCRF.

## 5.7 IVUS assessment

The secondary endpoint for the clinical study will be the distance from the proximal stent edge to the true ostium as measured by IVUS following stent deployment. The aorto-ostium will be defined as the plane at which the coronary artery joined the aorta sinus. Protrusion of the stent beyond this plane (*protruding stent*) as well as the distance between this plane and the most proximal stent strut (*geographical miss*) will be measured. In the case of side branches (left anterior

descending or circumflex) the ostium will be defined as the plane between the side branch emerging point and the carina tip. Protrusion of the stent beyond this plane (*protruding stent*) as well as the distance between this plane and the most proximal stent strut (*geographical miss*) will be measured.

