### 1.1 Clinical need

Accurate placement of coronary stents in ostial locations is known to be challenging (1). Angiographic ostial location ambiguity, often requiring multiple views, and problems with the motion of the stent before deployment are considered possible relevant sources of mistakes during PCI (2). Advancement of the stent past the ostium can lead to "geographic miss" where suboptimal scaffolding of the plaque or lack of coverage of areas exposed to balloon injury increase the risk of restenosis (3-5). If the stent is protruding in the donor vessel, it may cause difficulties, including 1) The need to re-cannulate the coronary artery, 2) a possible re-wiring through the side of the stent (in case of re-intervention) with subsequent stent deformation, and 3) unopposed struts undergoing an irregular process of endothelialization and neointima coverage (6,7). Of note, a retrospective analysis of 100 consecutive PCI of aorto-ostial lesions observed stent misplacement (defined as a stent deployed > 1 mm from the ostium) in 54% of cases, of which proximal and distal misses were equally represented (8). Interestingly, a geographic miss was associated with higher rates of restenosis and target lesion revascularization (TLR) compared with 'accurate' stent placement.

The use of robotic PCI is able to offer some advantages compared to manual PCI, including the reduction of longitudinal 'geographic miss' and the possibility of performing 1-mm accommodations in device positioning. In addition, it can improve lesion length evaluation as previously reported (9). The adjunct role of robotic-PCI in improving lesion coverage during ostial vessels PCI has never been previously evaluated.

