**Primary endpoints:**

- 1) Evidence of full ostial coverage at angiographic and IVUS assessment

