**Secondary endpoints:**

- 1) Distance from most proximal stent strut and coronary ostium (mm), as assessed by IVUS
- 2) In-hospital major cardiovascular events
- 3) Procedural duration (defined as the duration from when the sheath is inserted until it is removed)
- 4) Major adverse cardiovascular events at 1 month follow-up

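### Geographical miss is measured at the most proximal strut, the smallest gap around the rim, so a recorded 0 mm does not exclude uncovered ostium

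*Combined protocol and SAP*

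**What the plan says.** Section 2.1 lists as secondary endpoint 1 the "Distance from most proximal stent strut and coronary ostium (mm), as assessed by IVUS". Section 5.7 opens by describing this endpoint as "the distance from the proximal stent edge to the true ostium as measured by IVUS following stent deployment", without saying which point of the edge is meant. It then has two quantities measured: protrusion of the stent beyond the ostial plane, and geographical miss, which is "the distance between this plane and the most proximal stent strut". The same wording is used for aorto-ostial lesions and for side branches.

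The plane differs by lesion type. For aorto-ostial lesions, "The aorto-ostium will be defined as the plane at which the coronary artery joined the aorta sinus". For the left anterior descending and circumflex, "the ostium will be defined as the plane between the side branch emerging point and the carina tip". Neither definition makes the plane perpendicular to the stent axis. The documents do not ask for a reading at the least covered point or around the circumference, and they give no rule for a stent edge that is not parallel to the plane.

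The primary endpoint in section 2.1 is separate: "Evidence of full ostial coverage at angiographic and IVUS assessment". It has no operational rule and is not linked to the section 5.7 distance.

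**The concern.** Coverage of an ostium is a property of the whole rim, so the quantity that shows whether something was missed is the largest gap between the ostial plane and the stent edge. The most proximal strut gives the smallest gap. It is the right landmark for the greatest protrusion and the wrong one for a miss. If that one strut reaches the plane, the recorded miss is 0 mm whatever happens on the opposite wall. If it crosses the plane, the case is recorded as protruding, although the other side may be bare.

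At stake is the meaning of secondary endpoint 1. As written, a value of 0 mm says only that the stent reached the ostial plane somewhere. It cannot support a statement that the ostium was not missed.

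**Working it through.** **The plan's own figure first.** Section 3 gives 66 subjects for 80% power at the 5% level, with a miss rate of 50% and a 70% reduction, that is 0.50 × (1 − 0.70) = 0.15.

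- Two-sided comparison of two proportions, mean rate 0.325: n = [1.96 × √(2 × 0.325 × 0.675) + 0.8416 × √(0.50 × 0.50 + 0.15 × 0.85)]² / 0.35² = (1.298 + 0.517)² / 0.1225 ≈ 26.9, so 27 per arm.
- With continuity correction: n′ = (26.9 / 4) × [1 + √(1 + 4 / (26.9 × 0.35))]² ≈ 32.4, so 33 per arm and 66 in total.

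The stated figure is reproduced exactly, and nothing below changes it.

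**Geometry of the landmark.** The vessel diameter D and the tilt θ between stent edge and ostial plane are assumptions; neither is in the documents. Let φ be the angular position around the rim, starting at the best covered point, and let g₀ be the gap there. Measured along the stent axis:

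g(φ) = g₀ + (D / 2) × tan θ × (1 − cos φ)

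The smallest gap is g₀, at φ = 0. The largest is g₀ + D × tan θ, on the opposite wall. The section 5.7 landmark records g₀. When the most proximal strut lies on the plane, g₀ = 0 and the recorded miss is 0 mm for every tilt, while the opposite wall is uncovered by D × tan θ:

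| D (mm) | θ = 10° | θ = 20° | θ = 30° |
|---|---|---|---|
| 2.5 | 0.44 | 0.91 | 1.44 |
| 3.0 | 0.53 | 1.09 | 1.73 |
| 3.5 | 0.62 | 1.27 | 2.02 |
| 4.0 | 0.71 | 1.46 | 2.31 |

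For D = 3.0 mm and θ = 20° this is 3.0 × 0.364 = 1.09 mm. With no tilt the gap is zero and the landmark does no harm.

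For scale only, section 1.1 cites a retrospective series that reported "stent misplacement (defined as a stent deployed > 1 mm from the ostium) in 54% of cases". At D = 3.0 mm the hidden gap passes 1 mm when tan θ > 1/3, that is above about 18.4°. The trial does not adopt 1 mm as its own limit.

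**The protruding case.** If the most proximal strut lies beyond the plane by p, the largest gap is D × tan θ − p. With an assumed p of 0.5 mm in the same example, 1.09 − 0.50 = 0.59 mm of the far wall is still uncovered, and the subject is recorded as protruding.

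**Where the tilt comes from.** The result is the same whether the stent edge is oblique or the plane is. If the edge is square to the vessel axis and the plane is tilted, all edge struts share one axial position, and the frame with the most proximal strut is also the first frame with struts all round. A rule based on that frame would therefore recover none of the gap. The gap has to be read from the plane to the edge at the same angular position.

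**The case against.** The strongest reply is that this concerns one secondary measurement and goes no further. Section 5.7 presents the distance as the secondary endpoint. The primary endpoint is a separate judgement by angiography and IVUS, and an ostium bare on one side is not fully covered on a plain reading, so the primary endpoint can catch the very case described. A distance of 0 mm with incomplete coverage is then no contradiction, because the two endpoints record different things. This stands.

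A reader might also infer that the trial is undersized, because section 3 is worded in terms of geographic miss and section 5.7 holds the only working definition of that term. The documents do not support that step. Nowhere do they say that the single-strut distance decides who counts as a miss, and the share of misses hidden by the landmark is unknown. Purely as a conditional figure, suppose the distance did decide and a share of true misses scored zero equally in both arms. The uncorrected normal-approximation power at 33 per arm would then move from 87.7% to 81.8% at an assumed share of 10%, and to 66.7% at 30%. These figures rest on two assumptions that the plan does not make, and they form no part of the conclusion.

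It is also fair to say that the documents do not give the frequency or size of tilt, and give no reason for it to differ between arms. Finally, section 5.7 already measures both protrusion and miss, and its opening reference to the stent edge can be read as general wording that the later text makes specific. That is so, but the specific landmark is the one that gives the smallest gap, so this reading does not remove the problem.

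**Conclusion.** The point holds for geographical miss in section 5.7 and for secondary endpoint 1. The stated landmark gives the smallest gap around the rim, so a recorded 0 mm or a protruding stent is compatible with uncovered ostium whenever edge and plane are not parallel. That much follows from the definition alone.

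Its size in any subject depends on diameter and tilt, which are assumed here: about 1.1 mm for a 3 mm vessel at 20 degrees, 0.91 to 1.46 mm for 2.5 to 4.0 mm at that tilt, and nothing without tilt. How often it would occur cannot be determined from the documents.

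Three stronger readings are not supported: that the sample size of 66 is wrong, that the primary endpoint is biased, and that the comparison between arms is distorted.

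**What to change.** In section 5.7 and in secondary endpoint 1 of section 2.1, give each quantity its own landmark:

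- **Geographical miss:** the largest distance, around the circumference, from the ostial plane to the stent edge at the same angular position. For side branches, read it at least on the carina side and on the opposite wall.
- **Protrusion:** the distance by which the most proximal strut lies beyond the plane.

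Report the two as separate values from the same IVUS pullback. Do not use the first frame with struts around the full circumference as the landmark for miss, because it does not capture a tilted plane. In the primary endpoint, state that full coverage on IVUS requires the largest gap to be zero, so that the two endpoints fit together.

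The cost is a change of wording and one extra reading per existing pullback. The observed miss may be higher in both arms. No extra imaging or subjects are needed, and the sample size calculation stays as it is.
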